7. Any physical therapy such as cryosurgery, laser therapy, electrodesiccation, microdermabrasion, surgical removal of lesions, curettage, or treatment with chemical peels such as trichloroacetic acid inside or in close proximity (< 10 cm distance) to the treatment field within 4 weeks prior to screening.
8. Any of the topical treatments defined below within the designated periods prior to screening:
 - a. Topical treatment with ALA or ALA esters (e.g. methyl aminolevulinic acid (MAL)) or an investigational drug in- and outside the treatment field within 8 weeks.

- b. Topical treatment with immunosuppressive, cytostatic or cytotoxic drugs inside or in close proximity (< 10 cm distance) to the treatment field within 8 weeks.
- c. Start of topical administration of a medication with hypericin or other drugs with phototoxic or photoallergic potential inside or in close proximity (< 10 cm distance) to the treatment field within 4 weeks. Subjects may, however, be eligible if such medication was applied for more than 4 weeks prior to screening without evidence of an actual phototoxic/photoallergic reaction.

9. Any use of the systemic treatments within the designated periods prior to screening:

- a. Cytostatic or cytotoxic drugs within 6 months.
- b. Immunosuppressive therapies or use of ALA or ALA esters (e.g. MAL) within 12 weeks.
- c. Drugs known to have major organ toxicity within 8 weeks or an investigational drug.
- d. Interferon or glucocorticosteroids within 6 weeks.
- e. Start of intake of medication with hypericin or systemically acting drugs with phototoxic or photoallergic potential within 8 weeks prior to screening. Subjects may, however, be eligible if such medication was taken in for more than 8 weeks prior to the screening visit without evidence of an actual phototoxic/photoallergic reaction.

10. Breast feeding women.

11. Suspicion of drug or alcohol abuse.

12. Subjects unlikely to comply with protocol, e.g. inability to return for visits, unlikely to complete the study, or inappropriate in the opinion of the investigator.

13. A member of study site staff or sponsor staff directly involved in the conduct of the protocol or a close relative thereof.

14. Simultaneous participation in another clinical study.

Re-screening of subjects is allowed once in case exclusion criterion 3 is met and eligibility can be achieved within 14 days.

Dosing day exclusion criteria

At Visit 2 (baseline, PDT-1)

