4.2 Study rationale

Current FDA-approved treatment options for field-directed treatment of AK on the face and scalp are formulations containing diclofenac/hyaluronic acid (3 %/2.5 %), imiquimod cream (3.75%) or 5-fluorouracil, which require repeated applications for up to several months or lead to side effects related to erosive and/or inflammatory reactions induced by the treatment that may last for the entire treatment period or even longer (18–20).

Compared to methods like surgery, abrasion, cryosurgery, and alternative topical treatments, the use of PDT is advantageous for the field-directed treatment especially due to the high selectivity of treatment, but also to the short treatment period that is entirely controlled by the physician, and the excellent cosmetic results (21).

In addition, a European network meta-analysis of the relative clinical efficacy of 10 different treatment modalities for mild to moderate AK on the face and scalp, including PDT products as well as formulations containing cryosurgery, 5-fluorouracil, imiquimod, ingenol mebutate or diclofenac/ hyaluronic acid, has shown that ALA PDT using BF-200 ALA was the most efficacious treatment option (22).

Besides Ameluz[®], only one PDT product containing ALA is available in the US market. Levulan[®] Kerastick[®] providing ALA at a concentration of 20 % in a 2-component system that requires ALA to be compounded immediately before use. By label, the use of Levulan[®] Kerastick[®] is restricted to lesion-directed treatment of minimally to moderately thick AKs located on the face and scalp or the upper extremities. Ameluz[®] is the only PDT product available in the US market which has been approved for the field-directed treatment of AKs, but at the current time its label is restricted to the application of one tube of Ameluz[®].

In contrast to the currently marketed BF-RhodoLED[®] lamp the BF-RhodoLED[®] XL enables the illumination of a larger skin area in one step. The BF-RhodoLED[®] XL has 5 LED panels which are positioned in a curved shape.

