9.2 Prior and concomitant medications/treatments

Any medication taken by a subject or treatments the subject is undergoing that are not related to any study-specific procedures (PDT with IMP), starting with the time of signing the informed consent until the end-of-study are considered concomitant medications or treatments. The use of required concomitant medications or treatments, which are known not to interfere with the IMP or to mask its effect, is unrestricted and may be continued during the study.

The following treatments are examples for permitted treatments in the designated time periods to alleviate pain and discomfort (please consider the information provided in the respective PIs). Other treatments are also allowed as long as they are not explicitly forbidden in [Table 4](#):

- Prior to illumination
 - Acetaminophen (e.g. Tylenol®), ibuprofen up to 1200 mg per day, aspirin up to 3750 mg per day, ice gel/spray and/or application or injection of a local, fast-acting anesthetic, such as xylocaine or lidocaine.
- During illumination
 - In cases where the pain is regarded as unbearable by the subject, the illumination may be interrupted and/or cooling with an air stream and/or nebulized water may be offered.
 - Severe cases of pain might require to briefly interrupt illumination, e.g. to inject or apply a local, fast-acting anesthetic, such as xylocaine or lidocaine or to cool briefly with cooling packages.
- Treatment of pain and discomfort post illumination
 - Cooling the illuminated area(s) with wet or refrigerated compresses
 - Analgesic treatment with acetaminophen (e.g. Tylenol®) or NSAIDs (ibuprofen up to 1200 mg per day / aspirin up to 3750 mg per day)
 - Application of an analgesic cream

All concomitant medications/treatments or relevant concomitant medications/treatments taken/underwent during the study, must be documented in the eCRF along with the indication, route of administration, single dose, frequency of administration, as well as start and stop date of administration. The subject should confer with the investigator prior to the use of new medication until the end of the study.

The following concomitant treatments/procedures are not permitted:

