- Any therapy such as cryosurgery, laser therapy, electrodesiccation, surgical removal of lesions, curettage, or treatment with chemical peels such as trichloroacetic acid inside or in close proximity (< 10 cm distance) to the treatment field 4 weeks prior to screening until end-of-study. Lesions may be treated with these methods if the distance to the treatment field is more than 10 cm.
- A list of forbidden, concomitant medication is provided in [Table 4](#).

If the investigator, at any time in the study, suspects a lesion inside or outside the treatment field to have progressed into a manifest malignancy, they should refer the subject for standard medical treatment, irrespective of whether or not this results in exclusion of the subject from the study.

Table 4: List of forbidden concomitant medication with designated time periods.

Medication	Topical administration		Systemic administration	
	start of restriction	forbidden until	start of restriction	forbidden until
ALA or ALA-esters (except IMP at Visit 2)	8 weeks prior to Visit 1	end-of-study	12 weeks prior to Visit 1	end-of-study

Medication	Topical administration		Systemic administration	
	start of restriction	forbidden until	start of restriction	forbidden until
Cytotoxic drugs/ Cytostatic drugs	8 weeks prior to Visit 1 inside or in close proximity (< 10 cm distance) to the treatment field	end-of-study inside or in close proximity (< 10 cm distance) to the treatment field	6 months prior to Visit 1	end-of-study
Immunosuppressive therapies	8 weeks prior to Visit 1 inside or in close proximity (< 10 cm distance) to the treatment field	end-of-study inside or in close proximity (< 10 cm distance) to the treatment field	12 weeks prior to Visit 1	end-of-study
	7 days prior to PDT inside and outside the treatment field	7 days post PDT inside and outside the treatment field		
Interferon	---	---	6 weeks prior to Visit 1	end-of-study
Glucocorticosteroids	(allowed)	(allowed)	6 weeks prior to Visit 1 ^a	end-of-study ^a
NSAIDs (others than listed below)	7 days prior to PDT	7 days post PDT	7 days prior to PDT	7 days post PDT
Acetylsalicylic acid > 3750 mg/day	---	---	7 days prior to PDT	7 days post PDT
Ibuprofen > 1200 mg/day	---	---	7 days prior to PDT	7 days post PDT
Diclofenac	7 days prior to PDT within illumination area(s) ^b	7 days post to PDT within illumination area(s) ^b	> 100 mg/day; 7 days prior to PDT	> 100 mg/day; 7 days post PDT

Medication	Topical administration		Systemic administration	

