	start of restriction	forbidden until	start of restriction	forbidden until
Hypericin or drugs with phototoxic/ photoallergic potential^c	4 weeks prior to Visit 1 inside or in close proximity (< 10 cm distance) to the treatment field	end-of-study inside or in close proximity (< 10 cm distance) to the treatment field	8 weeks prior to Visit 1	end-of-study
Investigational drugs	8 weeks prior to Visit 1	end-of-study	8 weeks prior to Visit 1	end-of-study
Drugs known to have major organ toxicity	---	---	8 weeks prior to Visit 1	end-of-study
Medication that influence coagulation (e.g. anticoagulants, anti-platelet drugs)	---	---	Visit 1 (may be used throughout the study if taken in a stable dose prior to study)	end-of-study (may be used throughout the study if taken in a stable dose prior to study)
EMLA® cream	On day of PDT inside or in close proximity (< 10 cm distance) to the treatment field	On day of PDT inside or in close proximity (< 10 cm distance) to the treatment field	---	---

^a Not for inhaled glucocorticosteroids.

^b Topical use of diclofenac up to 2.5 % may be used outside illumination area(s) throughout the study.

^c Start of therapy with any photosensitizer or systemically-acting drugs with phototoxic or photoallergic potential, such as psoralenes, tetracyclines, nalidixic acid, furosemide, amiodarone, phenothiacines, chinolones, fibrates, or phytotherapy with St. John's wort, arnica, or valerian or topically applied phototoxic substances like tar, pitch, psoralenes or some dyes like thiazide, methylene blue, toluidine blue, eosin, rose bengal, or acridine within 4 weeks for topical administration or 8 weeks for systemic administration prior to screening. Subjects may, however, be eligible if such medication was taken longer than 4 weeks (topical) or 8 weeks (systemic) prior to screening without evidence of an actual phototoxic/photoallergic reaction.

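### Table 4 lifts the topical diclofenac restriction on the treated skin 7 days after PDT, three weeks before the nominal Visit 5, although the protocol itself names diclofenac as a field-directed AK drug

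*Protocol*

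**What the plan says.** Section 4.2 of the protocol lists the FDA-approved alternatives for field-directed AK treatment on the face and scalp: "formulations containing diclofenac/hyaluronic acid (3 %/2.5 %), imiquimod cream (3.75%) or 5-fluorouracil".

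Table 4 (Section 9.2) gives diclofenac its own row. The topical restriction starts 7 days before PDT and ends "7 days post to PDT within illumination area(s"). Footnote b adds: "Topical use of diclofenac up to 2.5 % may be used outside illumination area(s) throughout the study". That is the only strength limit on topical diclofenac.

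Other AK therapies are handled more strictly in the same section. Procedures and chemical peels are barred "inside or in close proximity (< 10 cm distance) to the treatment field 4 weeks prior to screening until end-of-study". Topical cytotoxic and cytostatic drugs are barred until "end-of-study inside or in close proximity (< 10 cm distance) to the treatment field".

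For pain and discomfort, Section 9.2 gives examples of permitted measures, including an analgesic cream after illumination, and then states: "Other treatments are also allowed as long as they are not explicitly forbidden in" Table 4.

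Exclusion 8b works by drug class: "Topical treatment with immunosuppressive, cytostatic or cytotoxic drugs inside or in close proximity" to the field within 8 weeks before screening. Imiquimod is named neither in exclusion 8 nor in Table 4.

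**The concern.** The plan treats other AK therapy on or near the treated skin as unacceptable up to the last visit, but sets a 7-day cut-off for a drug that it lists as an AK treatment. The strength rule also runs the wrong way: after Day 7, skin outside the illumination area carries a 2.5 % cap and the treated skin carries none.

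The study has one arm, so no control group can net out the local effects of a second drug. Application site reactions are defined in Section 10.2.7 as anything occurring in the field once PDT has started, and they are assessed up to Visit 5. The SAP's reaction table (4.4.1) and new-lesion tables (4.4.2) state no relatedness filter. A late local reaction to diclofenac, or an effect on new AK in or near the field, would therefore enter those tables.

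The SAP 4.6 data review discusses use of forbidden medication. Use that Table 4 does not forbid need not be raised there, and so would probably not reach the SAP 3.4 split of related TEAEs by major protocol deviation.

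**Working it through.** The plan gives no figure to reproduce: there is no sample size calculation and no hypothesis. The check is a reading of the rules, a count of days, and illustrative sizes.

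**Step 1: days without a listed restriction.** Inputs: restriction ends 7 days after PDT (Table 4); visit windows from Table 1. With PDT as Day 0 (the SAP numbers the treatment day as Study Day 1), unrestricted days = max(0, visit day − 8 + 1).

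| Visit | Earliest | Nominal | Latest |
|---|---|---|---|
| 3 | Day 5: 0 | Day 7: 0 | Day 9: 2 |
| 4 | Day 12: 5 | Day 14: 7 | Day 16: 9 |
| 5 | Day 21: 14 (14/21 = 67 %) | Day 28: 21 (21/28 = 75 %) | Day 35: 28 (28/35 = 80 %) |

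These are days on which nothing in Table 4 stands in the way. They are not days of observed use.

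**Step 2: could another row cover it?** The general NSAID row leaves out drugs with a row of their own, and it also ends 7 days after PDT. Footnote c, on phototoxic drugs, does not list diclofenac. No other topical row applies by name.

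**Step 3: why footnote b needs a distance limit.** The effective illumination area is at most 23 cm × 29 cm (Section 8.1.2). A square field of 60 cm² has a side of √60 ≈ 7.7 cm. Adding 10 cm on each side gives 27.7 cm, more than 23 cm. On a flat approximation, part of the < 10 cm ring, where new lesions are scored, lies outside the illumination area. There diclofenac up to 2.5 % is allowed throughout the study.

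**Step 4: illustrative size.** The documents give no number of users. Assume 1 to 5 of about 100 subjects.

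- One preferred term: at most 1/100 to 5/100, i.e. 1 to 5 percentage points.
- Any application site reaction: Section 4.3 reports 84–100 % of subjects with one in earlier trials. If use is independent of having a PDT reaction, each user adds (1 − 1.00)/100 = 0 to (1 − 0.84)/100 = 0.16 points; five users add 0 to 0.8 points.
- Mean duration: suppose one reaction present on Day 8 ends on Day 15 to Day 28 instead (+7 to +20 days), and 50 to 100 subjects have that term. The mean moves by 7/100 = 0.07 to 20/50 = 0.40 days. Section 4.3 gives 1 to 4 days as the usual duration. The SAP tabulates duration for related events only, so a late reaction rated unlikely related drops out.
- New AK counts: no size can be given.

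**Step 5: look-back if imiquimod gets the 8-week limit.** Counted from Visit 1, the limit is 56 days before PDT at the shortest and 56 + 14 (screening window) + 14 (one rescheduling of Visit 2) = 84 days at the longest.

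**The case against.** Table 4 is a list of what is forbidden, so silence is not permission. A reader might infer that the plan positively allows AK treatment with diclofenac on the field at any strength from Day 8. The documents do not support that. Section 9.2 leaves unrestricted only medication that the subject needs and that is known not to disturb or hide the effect of the IMP, and it adds: "The subject should confer with the investigator prior to the use of new medication until the end of the study". The open allowance for treatments missing from Table 4 covers relief of pain and discomfort only. The bar on procedures opens with general wording before its examples, so it could be read as a catch-all. However, every example is a procedure or a peel, exclusion 7 introduces nearly the same list as physical therapy, and drugs are referred to Table 4.

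Diclofenac also sits among the NSAID rows, all of which run from 7 days before to 7 days after PDT, and footnote b could be taken to confine use throughout the study to skin outside the illumination area. That reading is possible, but the cell itself ends the restriction at Day 7.

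On imiquimod, a reader might infer that the plan lets it through. The documents do not establish this: the rules work by class, 5-fluorouracil is not named there either, and neither document says which class imiquimod belongs to. Prior AK therapy in the treatment area is recorded at screening, and irritated skin within 10 cm excludes a subject at screening and on the dosing day. This part is a clarification, not a shown loophole.

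Other controls also count. Medication is recorded with indication, route and dates; causality assessment must weigh other drugs; SAP 4.2 tabulates concomitant medication by ATC level; Section 8.3 prefers that lesions outside the field wait until after Visit 5. The reaction table shows each subject's maximum intensity, so a late reaction raises it only if it exceeds the PDT peak. Section 4.2 does not specifically attribute erosive reactions to diclofenac.

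What remains is that all these controls rest on judgement or on description after the fact. None forbids the use, and for discomfort after Day 7 the wording allows it.

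**Conclusion.** The point holds as a minor inconsistency in the restriction rules. For 21 of 28 nominal days (67–80 % across the Visit 5 window) no listed restriction keeps topical diclofenac off the treated skin, while the plan protects that skin from other AK therapies to the end.

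It would be wrong to infer that the safety results are materially distorted. The study is descriptive, the number of users is unknown, and every effect size above rests on assumed users, denominators and prolongation. The effect is probably small and cannot be sized from the documents. Pain during illumination (NRS-11) and first-week reactions are protected from topical diclofenac by the existing restriction. The exposed data are late application site reactions, new-lesion tables and, only for events rated related, TEAE duration.

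**What to change.** In Table 4, keep the 7-day start before PDT for topical diclofenac, but set its end to end-of-study for skin inside or < 10 cm from the treatment field. Align footnote b so that diclofenac up to 2.5 % stays allowed only outside the illumination area and at least 10 cm from the field. This brings the unrestricted window on treated skin from 21 nominal days to 0, and any such use then falls under the forbidden-medication item of the SAP 4.6 review.

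At the same time, name topical imiquimod in exclusion 8b and in a matching Table 4 row: barred inside or < 10 cm from the field from 8 weeks before Visit 1 to end-of-study.

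The cost is a few lines of text; no new analysis, visit or subjects are needed. Diclofenac is lost as a local analgesic on and near the field from Day 8, but acetaminophen, ibuprofen, aspirin, cooling and other analgesic creams remain. A few recent imiquimod users would wait up to 8 weeks before screening. Other topical drugs, such as glucocorticosteroids (allowed) and other NSAIDs after Day 7, stay as they are; Section 4.2 does not name them as field-directed AK treatments.

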10 STUDY PROCEDURES AND SCHEDULE

All data obtained from subjects, e.g. assessments, questionnaires and examination results, should be sufficiently documented in source.

10.1 Description of study days

[Table 1](#) summarizes the study schedule.

10.1.1 Screening visit (≤ 14 days prior to PDT)

Potential subjects will be evaluated to determine if they fulfill the inclusion and exclusion criteria (see [Sections 7.3](#) and [7.4](#)).

Each subject will be assigned a six-digit subject number (consisting of a three-digit site number and a three-digit subject screening number) in the chronological order of enrollment within each site (e.g. 801-001). For this purpose, the next higher subject number is always assigned. This number will be documented and will be used to identify the subject. New subjects must always be assigned a new subject number.

The following procedures will be performed at Visit 1 (screening) and recorded in the eCRF:

- Obtain informed consent prior to any study-related procedures
- Assign subject number
- Obtain demographic data
- Document concomitant medical conditions and relevant medical history
- Document medical skin history (including NMSC (such as BCC, SCC or Bowens disease), melanoma, AK and other skin diseases)
- Document concomitant medications/treatments
- Document body measures
- Measure vital signs
- Physical examination
- Neurological assessments
- Check inclusion and exclusion criteria
- Assess skin type according to Fitzpatrick, 1988 ([32](#))
- Select the treatment field and assess AK target lesions (size, number, location and clinical severity assessment according to Olsen et al., 1991 ([33](#))). In case of severe AK lesions, a biopsy must be taken for confirmation of diagnosis.
- Generate graphic templates of the treatment field and location of AK target lesions on provided cartoon. The location of the treatment field and the AK lesions within in the treatment field as well as any AK lesions in close proximity (< 10 cm distance) to the treatment field should marked on a grid foil for re-identification during the course of the study.

- Clinical laboratory tests (including routine hematology and blood chemistry, serum pregnancy test for females of reproductive potential, and urinalysis). Please document if the subject was in a fasted state or not.
- Documentation of (S)AEs.
- Instruct subject about forbidden concomitant medications/treatments (see [Section 9.2](#) and [Table 4](#)).

10.1.2 Visit 2/ Baseline/ Treatment (PDT)

The following procedures will be performed at Visit 2 and recorded in the eCRF:

- Re-evaluation of inclusion and exclusion criteria for confirmation of subject's eligibility
- Evaluation of dosing day exclusion criterion
- Neurological assessments prior to PDT and 60 (± 10) min after end of illumination
- Skin assessment regarding new lesions (AK, NMSC, and melanoma) inside or in close proximity (< 10 cm distance) to the treatment field. NOTE: Occurrence of NMSC and melanoma will lead to exclusion of the subject
- Pregnancy test (urine) for females of reproductive potential prior to PDT
- Measurement of vital signs after subject's arrival at the site, within 10 min before start of illumination, within 10 min after end of illumination and 60 (± 10) min after end of illumination
- Preparation of the treatment field and administration of study medication (3 tubes) should be applied to a total area of approx. 60 cm²), and after drying of the gel application of a light-blocking, occlusive dressing according to treatment description in [Section 8.3](#)
- Illumination of the treatment field with the BF-RhodoLED[®] XL lamp until a total light dose of 37 J/cm² is achieved (according to treatment description in [Section 8.4](#)). In case of a discontinuous treatment field all patches must be within one illumination area (see [Section 8.1.2](#))
- Assessment of application site pain during illumination via NRS-11
- Documentation of (S)AEs including application site skin reactions, application site discomfort, and new lesions. Application site skin reactions and application site discomfort should be assessed directly after illumination (within 10 min) and should be re-assessed 60 (± 10) min after end of illumination (occurrence and severity).
- Documentation of concomitant medications/treatments including medications/treatments for pain management that might be required prior to, during or post illumination (see [Section 9.2](#) and [Table 4](#))
- Inform subjects to avoid sunlight, prolonged or intense light (e.g., tanning beds, sun lamps) on the treatment field for approximately 48 hours following treatment whether exposed to illumination or not

- Explanation and handout of subject diary to document AEs, their impact on the subject's daily life, and concomitant medication until the end of the study

